5.1.2. Secondary study parameters/endpoints

The Quality of life of patients is assessed at enrolment, at one, three and six months by means of the EORTC QLQ C15 pal(33). This is a 15-item questionnaire developed by the European Organisation for research and treatment of cancer Quality of Life Group. The questions are answered on a scale from 1 to 4, in which the number 1 refers to “not at all”, 2 refers to “a little”, 3 refers to “quite a bit” and 4 refers to “very much”. The EORTC QLQ C15 pal is a shorted version of the original EORTC QLQ C30 pal, which is specifically developed for palliative care. To optimize the feasibility of measures, this shortened version will be used to reduce the risk of missing items and decrease the burden on participating patients.

Symptom burden of patients is assessed at enrolment, at one, three and six months by means of the Utrecht Symptom Diary Four Dimensional (USD4D), which is a patient reported outcome measure (PROM)(34). The USD4D comprises of questions regarding the physical, psychological, social, and spiritual dimension, which are rated on a scale from 0-10 (0 = symptom is absent to 10 = severity symptom is the worst imaginable).

Primary caregiver burden is defined as the perceived burden of the individual that is faced with the primary responsibility of taking care of a disabled friend or loved one. The primary caregiver burden Is assessed at enrolment, one, three and six months by means of the Self Rated Burden Scale, which is a one item numerical scale answering the question “How do I perceive the care for my loved one at the moment?”(35–38). The question is answered on a scale of 0 to 10, in which 0 refers to “not at all straining” and 1 refers to “much to straining”. In

addition, the perceived burden of informal care (Dutch: Ervaren Druk Informele Zorg (EDIZ)) will be used, assessing aspects of informal care contributing to the perceived burden(39).

The EDIZ is developed for the use in caregivers of patients suffering from dementia at home, however, this measurement instrument is widely used to assess the level of burden of caregivers of patients with a life-limiting illness. This instrument contains 9 statements to which patients must answer “no!”, “no”, “more or less”, “yes” or “yes!”.

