6. STATISTICAL ANALYSIS

6.1. Primary study parameter(s)

To determine the effect of the SMEtH-intervention on the perceived symptom control after 1 month of patients of each nursing team, a mixed effects logistic regression analysis will be conducted. We will control for the following baseline measurements: age, gender, primary diagnosis, and performance status. Missing data are imputed using multiple imputation (MICE package in R) or if necessary, Bayesian imputation and analysis (Joint AI package in R). The quantitative data will be presented as odds ratio and 95% confidence interval (CI) in tables and graphs for the visualization of the results. Additionally, all analyses of primary and secondary study parameters are conducted by means of the statistical program RStudio, version 2022.12.0+353. (Vienna, Austria), and are considered statistically significant if $\alpha \leq 0.05$.

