6.2. Secondary study parameter(s)

Primary caregiver burden, symptom burden and quality of life of patients will be analyzed longitudinally using joint models for longitudinal analyses per symptom. Due to the fragility of the population, censoring of data will increase over time. Therefore, we will control for death, as well as age, gender, primary diagnosis, and performance status. Additionally, subgroup analyses for gender, age and primary diagnosis will be conducted for each secondary study parameter.

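### One 0.05 significance rule covers all secondary, per-symptom and subgroup analyses, with no multiplicity control, exploratory label or stated interaction test

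*Protocol*

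**What the plan says.** Protocol section 6.1 closes with a sentence that reaches beyond the primary endpoint: "all analyses of primary and secondary study parameters are conducted by means of the statistical program RStudio", and in the same sentence these analyses "are considered statistically significant if $\alpha \leq 0.05". No secondary analysis is exempted.

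Protocol section 6.2 sets the secondary analyses: "Primary caregiver burden, symptom burden and quality of life of patients will be analyzed longitudinally using joint models for longitudinal analyses per symptom". It adjusts for death, age, gender, primary diagnosis and performance status, and then states that "subgroup analyses for gender, age and primary diagnosis will be conducted for each secondary study parameter". It does not list the symptoms or scales to be modelled, the subgroup cut-points, or whether a subgroup analysis means a separate test in each stratum or an interaction term.

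Protocol section 5.1.2 names the instruments behind these outcomes: the EORTC QLQ-C15-PAL for quality of life, the USD4D for symptom burden, and the Self Rated Burden Scale and EDIZ for caregiver burden. Of the USD4D it says "The USD4D comprises of questions regarding the physical, psychological, social, and spiritual dimension", without giving the number of items.

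The document filed as the SAP is a data management plan. Its project abstract restates only the primary model. Its section 6 lists an analysis plan among the documents to be made available, but the content of that plan is not included.

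**The concern.** A threshold of 0.05 limits false positives to one in twenty for one test. Here the same threshold is attached to a family of unstated size: several outcomes, split by symptom, each examined again by three subgroup factors. Followed as written, the plan lets every p-value at or below 0.05 in that family be reported as statistically significant, with no advance list of which results were meant to count.

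The subgroup analyses raise a second issue. If they are run as separate tests within strata, a significant result in one stratum and a non-significant result in another does not show that the effect differs between them. Only an interaction addresses that question, and the plan does not say that one will be used.

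What is at stake is the reliability of individual symptom and subgroup claims, not the primary result.

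**Working it through.** **The plan's own figures.** The documents give no test count and no familywise error rate for the secondary analyses, so there is nothing of that kind to reproduce. The error rate in section 4.4 (alpha 5%, power 80%) sizes one comparison, 40% versus 30% on the primary endpoint. With 20 patients per cluster and ICC 0.001 the design effect is 1 + 19 × 0.001 = 1.019. A pooled-variance test with a noncentral t on 2(k − 1) degrees of freedom then needs k = 20 clusters per arm, as stated. The same method matches all eight rows of Table 1. That calculation does not cover the secondary analyses.

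**Inputs.**
- Level per test: 0.05 (section 6.1). Sidedness is not stated. Two-sided is assumed, consistent with the 95% confidence intervals in 6.1.
- Subgroup factors: three (section 6.2). The number of levels is not given. Two per factor is assumed, the minimum, which gives six strata.
- Three outcomes besides symptom burden: quality of life counted once, Self Rated Burden, and EDIZ (section 5.1.2).
- Symptom outcomes: not given. Two low counts can be taken from the protocol: the four USD4D dimensions (5.1.2) and the six common symptoms listed in section 1. Counts of 10 and 20 are assumptions.
- One treatment test per outcome. The nurse and GP questionnaire in 5.1.2 is left out.

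**Formulas.** With E outcomes, the number of tests M is E × (1 + 3) = 4E if each factor is assessed by one interaction test, or E × (1 + 6) = 7E if each stratum is tested separately. If PR has no effect, the expected number of nominally significant results is 0.05 × M. If the tests were independent, the chance of at least one is 1 − 0.95^M.

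| Outcomes E | M (interaction / within-stratum) | Expected false positives | Chance of at least one, if independent |
|---|---|---|---|
| 4 instruments, per-symptom wording set aside | 16 / 28 | 0.80 / 1.40 | 56% / 76% |
| 4 dimensions + 3 = 7 | 28 / 49 | 1.40 / 2.45 | 76% / 92% |
| 6 symptoms + 3 = 9 | 36 / 63 | 1.80 / 3.15 | 84% / 96% |
| 10 symptoms + 3 = 13 (assumed) | 52 / 91 | 2.60 / 4.55 | 93% / 99% |
| 20 symptoms + 3 = 23 (assumed) | 92 / 161 | 4.60 / 8.05 | over 99% for both |

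**Correlation.** Symptoms are likely to be correlated and the subgroups overlap. This leaves the expected number unchanged but lowers the chance of at least one and makes false positives cluster. For the overall tests alone, 13 independent tests give 1 − 0.95^13 = 49%, against 38% in a simulation with an assumed exchangeable correlation of 0.4. For 23 tests the figures are 69% and 52%. The value 0.4 is not from the documents.

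**Direction.** With two-sided tests, about half of the false treatment effects favour PR. On the within-stratum reading that is 2.45/2 to 3.15/2, about 1.2 to 1.6, for 7 to 9 outcomes, and 4.55/2 to 8.05/2, about 2.3 to 4.0, for 13 to 23. A false interaction points to a subgroup rather than to an arm.

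**The case against.** The plan does have a hierarchy of a kind. It names one main parameter at one month, gives it its own model, and labels everything else secondary. Many readers treat secondary and subgroup results as supportive without being told. The primary test keeps its 5% error rate whatever happens in section 6.2. All of this stands, and it limits the point to the secondary claims. It does not remove it, because section 6.1 gives secondary results the same significance rule as the primary instead of a supportive status.

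A separate analysis plan may settle the matter. The data management plan refers to one, so absence can be shown only for the two documents supplied. The protocol's stated rule still needs correcting there.

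Three stronger inferences are tempting, and the documents do not support them:
- A reader might infer that five to eight false positives are to be expected. That needs both 10 to 20 symptoms, which is an assumption, and separate tests within strata, which section 6.2 does not specify. Counts built from the protocol's own figures give 1.4 to 3.2, and the instrument-level floor gives 0.8 to 1.4, although that floor disregards the per-symptom wording.
- A reader might infer that the plan commits to within-stratum tests, so that an effect in women but not in men becomes a finding. The text permits this but does not require it. The supportable criticism is that the method is unspecified.
- A reader might infer that a symptom or subgroup result will carry the conclusion if the primary is null. Nothing in the documents says so.

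**Conclusion.** The point holds as a cheap improvement. A stated rule, 0.05 for all primary and secondary analyses, is applied to per-symptom models and three subgroup factors with no multiplicity control, no exploratory label and no stated use of interaction. The consequence is a small number of chance findings that the plan would call significant: on counts built from the protocol's own figures, about 1.4 to 1.8 with interaction tests and 2.5 to 3.2 with within-stratum tests. On the assumed larger symptom counts the ranges are 2.6 to 4.6 and 4.6 to 8.1.

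These figures rest on no true effect of PR on any outcome, one test per outcome, two levels per subgroup factor, and quality of life counted once. More subgroup levels under separate testing, or item-level analysis of the quality-of-life questionnaire, would raise them. Analysis at instrument level would lower them.

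**What to change.** In section 6.1, restrict the 0.05 significance rule to the primary endpoint.

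In section 6.2, keep the planned longitudinal joint models, but state that secondary, per-symptom and subgroup results are exploratory and are reported as estimates with 95% confidence intervals and no significance claim. List the symptoms and scales to be modelled and the subgroup categories. Assess each subgroup factor by an arm-by-subgroup interaction with its confidence interval, not by separate tests within strata.

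If the sponsor wants a confirmatory secondary claim, it should name those few outcomes in advance with a multiplicity procedure of its choice. For scale, one summary result for each of the four instruments under Bonferroni would be tested at 0.05/4 = 0.0125. Keeping all 63 tests of the nine-outcome within-stratum case confirmatory would need 0.05/63 = 0.00079 each.

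The cost is protocol and analysis-plan wording, with no extra patients, visits or data. The downside is that fewer secondary results can be called significant.

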6.3. Other study parameters

To provide characteristics of patients, primary caregivers, individual nurses, nursing teams and GPs at baseline, descriptive statistics will be used and displayed in tables.

7. ETHICAL CONSIDERATIONS

7.1. Regulation statement

This study will be performed according to GDPR (AVG), WGBO and code of conduct.

The risk of adverse health effects if patients participate is low since the intervention focuses on the methodological application of nursing essential care symptom management. In other words, it does not impose specific interventions to each participant, it rather is a systematic approach and deployment of current guidelines in palliative care.

As sign of gratitude for participating in the study and to ensure uniformity of practice within both healthcare organizations, all control groups will be offered the intervention after completing the study.

7.2. Recruitment and consent

Recruitment and consent of participants takes place on multiple levels:

Home care organizations will be recruited from a convenience sample of existing cooperation partners of the University Medical Centre Utrecht and from interested home care organizations. Contact with the organizations will take place through mail and telephone. If directors of the organizations consent to participation, regional and team managers will be contacted for further information. Information regarding this study will be provided digitally and verbally, however, the local routing of consent can alter per organization depending on the structures of the organization.

After consent of the home care organizations, team managers will receive written information about the study and if a team is interested, an information session will be organized to provide detailed information. During and after the information session, nursing teams will have the opportunity to ask questions that arise from the provided information. Verbal and oral consent for participation of a nursing team will be given by each team manager of the corresponding team.

The attending nurse and a contact person of each nursing team will screen patients on eligibility, to ensure a structured patient selection. During the study period the cohort will be accessible for the enrolment of new patients that meet the inclusion criteria. Eligible patients will be approached and asked by the attending nurse to participate. In case of a positive response, the nurse will ask the patient for permission to share their contact details with the research team to receive further information regarding the study. Patients will receive oral and written information and detailed participant information forms. The need for additional information or questions arising from the provided information will be answered by the

researchers in person or by telephone. After obtaining the written informed consent of the patient and the primary caregiver, both will be enrolled in the study. In case of unwillingness to participate in the study by a family caregiver, a patient still can be enrolled if desired.

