4.2 Inclusion criteria

Patients are eligible if:

1. patient is 18 years or older.
2. The patient is diagnosed with a life limiting illness or frailty syndrome with a life expectancy of less than a year, estimated by the nursing team, based on the Surprise Question.
3. The patient lives at home.
4. The patient suffers from at least 1 symptom identified by means of the problem list of the Distress Thermometer.
5. The primary caregiver/informal caregiver is aged over 18 and able to speak and read Dutch.

A member of the nursing team is eligible if:

1. He/she working as a nurse assistant, registered nurse, specialized nurse, nurse practitioner or palliative care specialist consultant.
2. He/she is 18 years or older.
3. He/she works for at least 16 hours a week.

A nursing team of a participating homecare organizations is eligible if:

1. The nurses that are part of the nursing team are motivated to participate in the study.
2. The Nursing team has a total of ten or more patients under their care suffering from a life-limiting illness.

Chaplains, GPs, paramedics, social workers, and other healthcare professionals are eligible if:

1. He/she is 18 years or older.
2. He/she actively collaborates with one of the included nursing teams.

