Lastly, an assessment of demographic characteristics and perceived care burden on the primary caregiver is performed by the research team. Thereafter, at one-, three- and six-months perceived care burden is evaluated by telephone using the EDIZ rating scale. After each assessment the primary caregiver will be offered support of a NP, specialised in PC to talk about possible thoughts or concerns raised by completing the questionnaires.

Blinding:

In causal studies, blinding is performed ideally at participant, data collection and data analysis level. In this case, however, blinding at the analysis level is the only feasible.

- The participants are not blinded. Patients, primary caregivers, and the nursing teams will all be aware of their allocation to the intervention group, since the method Palliative Reasoning will be implemented in daily care.
- The data collection will not be performed blindly. Firstly, the data are collected by local nurses who are aware of their allocation. Secondly, the research team who is involved in training the participants are also aware of the allocation, which is necessary to ensure an in-depth exploration of the experiences of the nursing team

during the up-following qualitative part of this study. This part will be described in a different research protocol, which is part of phase 4 of this study.

- Data analysis will be performed blinded. The researcher performing the data analysis will be blinded for the group allocation using labels. The labels will be opened after the analysis.

Randomization and allocation:

The clusters will be randomized through a simple randomization method with the Clinical Trial Randomization Tool from the National Cancer Institute(40,41). To minimize the risk of allocation bias, we will stratify between both homecare organization. The teams are informed about their allocation by the research team.

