1.15 Last check date by datamanager

2023-07-25

1.16 Indicate which laws and regulations are applicable for the project (please check all that apply)

- Richtlijn Kwaliteitsborging Mensgebonden Onderzoek (Quality Assurance for Research Involving Human Subjects)
- Nederlandse gedragscode wetenschappelijke integriteit
- Gedragscode Gezondheidsonderzoek (Dutch)
- Wet op de Geneeskundige Behandelingsovereenkomst (WGBO) or Medical Treatments Contracts Act
- Algemene Verordening Gegevensbescherming (AVG) or General Data Protection Regulation (GDPR)

2. Data Collection

2.1 Give a short description of the research data.

| Subjects | Volume | Data Source | Data Capture Tool | File Type | Format |
|----------|--------|----------------------|-------------------------------|-------------------|--------|
| Human | 500 | EPD | Secured server, Julius Centre | Quantitative data | .csv |
| Human | 50 | Questionnaires | Castor | Quantitative data | .csv |
| Human | 100 | Voice recordings | Secured server, Julius Centre | Qualitative data | m4.a |
| Human | 100 | Transcripts | Secured server, Julius center | Qualitative data | .doc |
| Human | 25 | observations/reports | Secured server, Julius Center | Qualitative data | .doc |

2.2 Describe the flow of the data (name systems used and/or third parties, recipients) <add link to location where diagram is stored in RFS>

Nursing teams and the contact person working at Icare and AxionContinu select eligible patients --> nursing teams ask patients and their family caregiver to fill in the surveys --> surveys are handed out to the research team through the contact person of each nursing team --> research team store the data in Castor and analyse the data with R and/or SPSS.

Alongside the effect study a process evaluation will be carried out. This process evaluation is not mentioned in the study protocol of SMEtH, but has its own individual protocol. The flow of the data for the process evaluation part of this study is as follows: Zorgbelang Inclusief will guide the discussions with the focus groups --> observations are made by the research team during the focus groups --> observations focus groups are reported in Word.

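### Teams that know their allocation select and first approach the patients, and identification training is described for the intervention arm only, so case mix can differ between arms

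*Protocol*

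**What the plan says.** **Who knows the allocation.** Protocol 5.2 says of the teams: "The teams are informed about their allocation by the research team". On blinding it adds: "Patients, primary caregivers, and the nursing teams will all be aware of their allocation to the intervention group". It does not say when teams are told.

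**Who selects patients.** Protocol 7.2: "The attending nurse and a contact person of each nursing team will screen patients on eligibility, to ensure a structured patient selection". It continues: "Eligible patients will be approached and asked by the attending nurse to participate". The research team gives further information only after a positive response to the nurse. Section 2.2 of the data management plan (supplied as the SAP) agrees: "Nursing teams and the contact person working at Icare and AxionContinu select eligible patients".

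**On what basis.** Protocol 4.2 requires a life expectancy of under a year, "estimated by the nursing team, based on the Surprise Question". It also requires a symptom: "The patient suffers from at least 1 symptom identified by means of the problem list of the Distress Thermometer".

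**How the arms differ.** Section 3 makes identification the start of the intervention, and section 2 makes it a secondary objective. Protocol 5.2 describes training in identification for the intervention group only. Control teams continue usual care (section 3).

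**When.** Protocol 5.2 puts team training first and patient baseline second. Enrolment stays open under 7.2: "During the study period the cohort will be accessible for the enrolment of new patients that meet the inclusion criteria".

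**Analysis.** Protocol 6.1 adjusts for age, gender, primary diagnosis and performance status. Symptom control is asked at enrolment (5.1.1) but is not a covariate. Baseline characteristics are tabulated (6.3).

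**The concern.** The trial sets out to improve, in one arm, the judgement that decides who enters the analysis. If the training works, intervention teams may list patients whom control teams would not. They might find people earlier and with milder problems, or find more people whose symptoms are uncontrolled. Knowing the allocation may also affect whom a nurse approaches.

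The one-month comparison would then mix any effect of symptom management with a difference in who was enrolled. Stratifying by organisation balances teams, not the choice of patients within them. Label-blinded analysis acts after selection. A larger sample would not remove the bias. Baseline tables can show measured imbalance among enrolled patients, but not whether it arose from identification, from approach or by chance. No patient list fixed before disclosure is described, and no log of patients screened, eligible or approached.

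**Working it through.** **1. The planned size.** Protocol 4.4 gives 30% v 40%, 80% power, alpha 5% (taken as two-sided), 20 patients per team and 20 teams per arm at ICC 0.001. I used design effect DE = 1 + 19 × ICC, pooled variance 2 × 0.35 × 0.65 and a t reference on 2(k − 1) degrees of freedom. This gives k = 25.65, 22.27, 20.57 and 19.22 teams per arm for ICC 0.02, 0.01, 0.005 and 0.001. Rounded up these are 26, 23, 21 and 20, as in Table 1. The four rows for 60% v 30% also match (5, 4, 4, 4). The planned size is therefore taken as it stands: 20 × 20 = 400 patients per arm.

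**2. The timing inference.** No sentence says that allocation is disclosed before patients are identified. The order of steps in 5.2 points that way, and anyone enrolled after a team is told is selected by people who know. Section 2.4 of the data management plan says data are gathered after implementation, but it is answering a question on reuse of existing data. The neighbouring table in 2.5 denies repeated measurements, contrary to Protocol 5.1.1 and 5.1.2. I give 2.4 little weight.

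**3. Illustrative size.** The documents give no figure for a case-mix shift, so these inputs are assumed. Suppose 4 of 20 patients per intervention team (20%) are of a kind that control teams would not list. Suppose also that, after the four covariates, their chance of symptom control differs by 10 to 20 points. The shift is 0.20 × 10 = 2 to 0.20 × 20 = 4 points.

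- Null SE = √(2 × 0.3 × 0.7 / 400 × DE). At ICC 0.001, DE = 1.019 and SE = 3.27 points. At ICC 0.02, DE = 1.38 and SE = 3.81 points.
- Rejection with no treatment effect = Φ(shift/SE − 1.96) + Φ(−shift/SE − 1.96).

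| Residual shift | ICC 0.001 | ICC 0.02 |
|---|---|---|
| 1 point | 6.1% | 5.8% |
| 2 points | 9.4% | 8.2% |
| 4 points | 23.1% | 18.3% |

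If the shift runs against the intervention, power for 40% v 30% (unpooled SE) falls from 84.0% to 66.1% and 43.3% at ICC 0.001, for 2 and 4 points. At ICC 0.02 it falls from 71.8% to 53.2% and 33.7%.

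**4. What baseline symptom control could do.** Assume the same gap exists at baseline and the two answers correlate at r = 0.3 to 0.5. In a linear approximation the shift becomes (1 − r) × shift and the SE is multiplied by √(1 − r²). Rejection falls to 6.4–14.6% at ICC 0.001 and 6.1–12.0% at ICC 0.02. That helps but does not close the gap.

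**5. Precision among patients listed before disclosure.** With an assumed 10 listed patients per team, DE = 1 + 9 × ICC = 1.009 or 1.18. Power for the full 10 points is 55.5% or 49.2%. With 15, DE = 1 + 14 × ICC = 1.014 or 1.28, and power is 72.7% or 62.6%. If only half the effect were present (assumed), power over these four cases is about 16 to 25%.

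**The case against.** The strongest reply is that the plan has safeguards.

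- The written criteria and the symptom requirement (4.2) are the same in both arms.
- Patients whose questionnaire shows no symptoms are excluded (5.2).
- Teams are expected to identify about twenty patients and enrol twenty (4.4). If so, there is little room to choose whom to approach.
- The four covariates in 6.1 are plausible carriers of case mix. If they removed 25 to 75% of a raw shift of 2 to 4 points (assumed), 0.5 to 3 points would remain, and false rejection at ICC 0.001 would be about 5 to 15%.

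These points reduce the concern without removing it. The criteria still pass through the team's judgement. One symptom sets a floor and does not equalise severity. Enrolling nearly all identified patients does not settle who is identified.

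Three stronger readings are tempting and not supported:

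- A reader might infer that all patients are identified after disclosure and training. The documents do not say so.
- A reader might infer that no screening record will exist. The supportable statement is that none is described; section 6 of the data management plan refers to an analysis plan that is not among these documents.
- A reader might infer a bias in favour of the intervention. The direction cannot be determined.

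There is also a fair objection to one natural remedy, approaching patients before disclosure. Implementation takes about a month, with coaching from two weeks after training (5.2), and the outcome is asked one month after enrolment (5.1.1). Patients enrolled that early could reach their assessment while the team is still being trained.

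**Conclusion.** The concern holds as a risk built into the plan. Team members who know their allocation can decide who is eligible and who is approached, and training in that judgement is described for one arm only. The resulting case-mix difference has unknown size and direction, and the planned adjustment may not remove it.

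The 9–23% (ICC 0.001) and 8–18% (ICC 0.02) error rates illustrate an assumed 2–4 point residual shift in a simple two-proportion test. They do not estimate the error rate of the mixed model in 6.1, and the error is smaller to the extent that the four covariates capture the shift. The plan should be changed, because a list made before disclosure cannot be rebuilt later. Confidence is medium: the mechanism is documented, while the timing is inferred and the size unknown.

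**What to change.** In Protocol 5.2, 6.1 and 7.2:

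1. **Dated list.** Before a team's allocation is disclosed, have it apply the Surprise Question and the other criteria that need no patient contact to its current caseload. Use one identical written instruction in both arms. Apply the symptom criterion later, as planned. Do not bring approach, consent or baseline forward for this purpose. Keep enrolment and one-month timing the same in both arms, and reconcile 5.1.1 with 5.2 on when the one-month clock starts relative to implementation.
2. **Log.** Record numbers screened, eligible, approached and consenting by arm, with reasons for listed patients not approached. Flag each enrolled patient as listed before or after disclosure.
3. **Baseline symptom control.** Report the one-month model with and without it. Pre-specify the adjusted model as primary if baseline is measured before the team's training. Otherwise present it as a sensitivity analysis, because baseline may already carry some intervention effect.
4. **Supporting analysis.** Fit the same model in patients listed before disclosure and state its lower precision: about 49–73% power with 10–15 listed patients per team if the full 10-point effect is present, and less if exposure is incomplete.

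**Cost.** Each team makes one caseload review. Protocol 4.2 already requires a count of ten or more patients with a life-limiting illness, so the Surprise Question review is additional but modest. Disclosure comes slightly later. Giving control teams the eligibility instruction narrows the contrast in identification somewhat, by an amount the documents do not allow to be sized; they must apply the Surprise Question for inclusion anyway. Baseline symptom control needs no new data. Patients who enter after disclosure remain unprotected, but the flag and log make this visible.
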